5. STATISTICAL METHODOLOGY

5.1. General Methodology

Unless otherwise noted, SAS[®] software (SAS Institute Inc, Cary, NC; v9.1 or later) will be used for the generation of all tables, graphs, and statistical analyses. Descriptive summaries for continuous variables will include, but not be limited to, the number of observations, mean, standard deviation, median, minimum, and maximum. Descriptive summaries for categorical variables will include the number and percentage of participants in each category.

5.2. Treatment Groups

This is a randomized, dose-escalation, placebo-controlled study. Up to 90-mg doses will be tested. Data will be summarized overall and by treatment group based on the dose regimen initially assigned.

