10.4. Statistical Analyses

10.4.1. Safety Analyses

Safety endpoints are listed in Section 3. Safety analyses will be conducted using the FAS population and are summarized in [Table 14](#).

Table 14: Safety Analyses

Endpoint	Statistical Analysis Methods
Primary	
Adverse Events
 
A TEAE is any AE either reported for the first time or worsening of a pre-existing event after first dose of study drug. Analysis of AEs will be limited to TEAEs, but data listings will include all AEs regardless of their timing to study drug administration. Adverse events will be coded using MedDRA and tabulated by preferred term and system organ class. Severity of AEs will be based on the CTCAE v4.03 using Grades 1 through 5.
 
The subset of AEs considered by the investigator to have a relationship to study drug will be considered to be treatment-related AEs. If the investigator does not specify the relationship of the AE to study drug, then the AE will be considered treatment-related. The incidence of AEs and treatment-related AEs will be tabulated.
 
Clinical Laboratory Tests
 
Actual values and changes from baseline in clinical laboratory test results will be summarized using descriptive statistics. Laboratory test values outside the normal range will be assessed for severity based on the normal ranges for the clinical reference laboratory. The incidence of abnormal laboratory values will be tabulated.
 
Laboratory data will be classified into Grades 1 through 4 using CTCAE v4.03. The following summaries will be produced for the laboratory data:
 
Number and percentage of participants with worst postbaseline CTCAE grade (regardless of baseline value) will be summarized. Each participant will be counted only for the worst grade observed postbaseline.
 
Shift tables from baseline to the worst postbaseline value using CTCAE grade.
 
For laboratory parameters where CTCAE grades are not defined, shift tables to the worst postbaseline value using the low/normal/high classifications based on laboratory reference ranges will be provided.
 
Vital Signs
 
Descriptive statistics and mean change from baseline will be summarized for vital signs (blood pressure, pulse, respiratory rate, and body temperature) at each assessment time.
 
Electrocardiograms
 
Twelve-lead ECGs will be obtained for each participant during the study. Electrocardiogram abnormalities, both at baseline and postbaseline visits, will be tabulated by treatment group. Incidences of abnormalities will be listed with study visit, assigned treatment group, and a description of the abnormality. Participants exhibiting clinically notable ECG abnormalities will be listed.

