2.2. Objectives and Endpoints

[Table 1](#) presents the objectives and endpoints.

Table 1: Objectives and Endpoints

Objectives	Endpoints
Primary	
To determine the safety and tolerability of INCB054707.	
 • Frequency, duration, and severity of AEs, clinical laboratory test results, vital signs results, ECGs, and physical examination findings.
Secondary	
To determine the systemic exposure to INCB054707.	
 • Population PK parameters of INCB054707.
To determine the efficacy of INCB054707.	
 • Proportion of participants achieving a HiSCR at each visit. • Proportion of participants achieving an AN count of 0 to 2 at each visit. • Mean change from baseline in the HS Pain NRS scores, worst and average pain, at each visit. • Mean change from baseline to Week 8 in the modified Sartorius scale score. • Mean change from baseline in the number of draining fistulas count at each visit. • Proportion of participants at each category of Hurley Stage at baseline and Week 8. • Proportion of participants with change from baseline in Hurley Stage at Week 8. • Proportions of participants in each HS-PGIC category during the treatment period. • Actual measurements in HS-PGIC at each visit.
To assess the need for rescue lesional treatment.	
 • Proportion of participants requiring rescue lesional treatment. • Number of interventions with rescue lesional treatment.
To assess patient-reported quality-of-life burden.	
 • Proportion of participants at each scoring category of DLQI at each visit. • Mean change from baseline in DLQI total scores at each visit.

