3.1. Randomization

The study includes 3 cohorts, and approximately 36 participants will be enrolled. In each cohort, approximately 12 participants will be randomized in a 3:1 ratio to receive either INCB054707 (n = 9) or placebo (n = 3).

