3.3. Sample Size Considerations

The study is a standard dose-escalation design, and the sample size depends on the occurrence of safety findings. Approximately 9 participants will be randomized in each dose level, which will provide > 85% chance of detecting at least 1 AE of interest (eg, platelets, hemoglobin, absolute neutrophil count, liver functions, and infections) if the underlying rate is 20%.

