5.3. Analysis Populations

5.3.1. Full Analysis Set

The FAS includes all participants enrolled in the study who received at least 1 dose of study drug.

The FAS will be used for the summary of demographics, baseline characteristics, participant disposition, and analyses of all efficacy and safety data.

[REDACTED]

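### The primary safety tables group participants by assigned treatment, with no visible exception, so a dispensing error would put adverse events under a treatment not taken

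*SAP*

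**What the plan says.** The grouping rule is in SAP 5.2: "Data will be summarized overall and by treatment group based on the dose regimen initially assigned". It makes no exception for safety.

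SAP 5.3.1 defines a single visible population: "The FAS includes all participants enrolled in the study who received at least 1 dose of study drug". It is used for "analyses of all efficacy and safety data". The protocol agrees in 10.4.1: "Safety analyses will be conducted using the FAS population". Table 14 there applies assigned grouping to the ECG listing: "Incidences of abnormalities will be listed with study visit, assigned treatment group, and a description of the abnormality". Every safety table in SAP Appendix A is on the FAS, and SAP 10.1 records no departure from the protocol.

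These tables report the primary endpoint (SAP 2.2): "Frequency, duration, and severity of AEs, clinical laboratory test results, vital signs results, ECGs, and physical examination findings".

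**The concern.** The FAS decides who is counted, not the column in which they are counted. The column comes from SAP 5.2, which follows assignment. For efficacy that is the usual choice. For a primary objective of safety and tolerability, the column should reflect what the participant took.

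Under the rule as written, a participant assigned placebo but given drug has any drug toxicity shown as a placebo event. A participant assigned drug but given placebo adds an unexposed person to a dose column. The exposure summary (SAP 6.4) is also by treatment group, so a placebo column could show active dose. With about 9 participants per dose and 3 placebo per cohort, one person is a visible share of a column.

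**Working it through.** **Inputs**
- About 9 participants per dose level and 3 placebo in each of 3 cohorts (SAP 3.1).
- A placebo column of 3 × 3 = 9. This assumes pooling across cohorts, which no visible text states.
- Event rate on drug 20%, and a stated detection chance above 85% (SAP 3.3).
- Background rate on placebo, p0. The documents give none, so it is assumed at 0, 5, 10 and 20%.
- One participant on the wrong treatment throughout. This is hypothetical.

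**1. The plan's own figure.** SAP 3.3 says: "Approximately 9 participants will be randomized in each dose level, which will provide > 85% chance of detecting at least 1 AE of interest". Check: 1 − 0.80^9 = 86.6%. It reproduces.

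**2. Expected rates after one error, grouped as assigned**
- Assigned drug, took placebo: drug column = (8 × 0.20 + p0)/9.
- Assigned placebo, took drug: placebo column = (8 × p0 + 0.20)/9.
- The shift is (0.20 − p0)/9 in either case, downward in the drug column and upward in the placebo column.

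| p0 (assumed) | Drug column (should be 20%) | Placebo column (should be p0) | Shift, points |
|---|---|---|---|
| 0% | 17.8% | 2.2% | 2.2 |
| 5% | 18.3% | 6.7% | 1.7 |
| 10% | 18.9% | 11.1% | 1.1 |
| 20% | 20.0% | 20.0% | 0 |

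**3. Ceiling on the observed shift.** Suppose the only event in the placebo column belongs to the participant who took drug. The rate is 1/9 = 11.1% as assigned and 0/8 = 0% as received, a shift of 11.1 points. If placebo is shown by cohort instead of pooled, the same case is 1/3 = 33.3 points.

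**4. Detection chance**
- Assigned drug, took placebo: the as-assigned column shows n = 9 with a chance of 1 − 0.80^8 × (1 − p0), which is 83.2%, 84.1%, 84.9% and 86.6% for the four values of p0. Grouped as received, the column shows the 8 truly exposed and 1 − 0.80^8 = 83.2%. Regrouping corrects the count and the label. It cannot restore the lost exposure.
- Assigned placebo, took drug: the as-assigned drug column stays at 9 (86.6%). Grouped as received, it has 10 exposed and 1 − 0.80^10 = 89.3%.

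**5. Direction.** After one error of either kind, the expected drug-minus-placebo difference is (8/9) × (0.20 − p0). At p0 = 0 it falls from 20 to 17.8 points. That is bias toward no difference in expectation, when drug raises the event rate. It need not hold in a given dataset. Suppose a placebo-assigned participant takes drug and has no event. As assigned, 2/9 − 1/9 = 11.1 points. As received, 2/10 − 1/8 = 7.5 points. Here the assigned grouping shows the larger contrast.

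**6. The escalation rule.** Protocol 6.5.2 ends escalation on dose-limiting toxicities (DLTs) in 3 or more participants of a cohort treated with INCB054707. It is worded by treatment taken and does not depend on SAP 5.2.

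**The case against.** The strongest reply is that this is contingent. Protocol 6.6.3 allows no dose modifications, so assigned and received treatment differ only by mistake. Assignment and supply run through a central web response system (Protocol 6.3, 8.1.3), with accountability records and tablet counts (6.2, 6.4). Deviations and study drug administration are listed (SAP 6.3, Appendix A), so an error could be noticed. All of this stands and keeps the point minor. None of it moves an event to the right column.

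The words about initial assignment may be standard text aimed at later dose changes. As written, they also govern a wrong kit. Protocol 10.2 is not visible and text after SAP 5.3.1 is redacted, so a received-treatment rule could exist there. It would then conflict with SAP 5.2 and need reconciling.

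A reader might infer that an error is likely. The documents do not support that, because they give no error rate. There are about 36 × 2 = 72 dispensings (Day 1 and Week 4). An assumed wrong-treatment rate of 0.5 to 1% each gives 1 − 0.995^72 = 30% to 1 − 0.99^72 = 51%. If the same rate means a wrong kit drawn at random under 3:1 allocation, only 2 × 0.75 × 0.25 = 37.5% of errors change treatment, and the range is about 13 to 24%. Nothing here rests on either range.

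**Conclusion.** The point holds as a minor gap in the analysis rules. On the visible text, an adverse event in a participant given the wrong treatment would be reported in the primary safety tables under a treatment not taken.

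- **Size, given one error:** about 2 points in expectation (drug rate 20%, background rate assumed 0%), less as the background rate rises, and at most about 11 points in a column of 9. The placebo figures assume pooling.
- **Direction:** toward no difference in expectation, when drug raises the event rate. A reader might infer that it always dilutes the contrast; the example in step 5 shows otherwise.
- **Reach:** the SAP's descriptive summaries. A reader might infer that dose decisions are affected too, but the escalation rule follows treatment taken, and population PK is reported separately (Protocol 10.4.3).

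If no error occurs, nothing changes.

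**What to change.** In SAP 5.2, with a matching line in 5.3.1, state that:

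1. Safety and exposure summaries group participants by treatment actually received.
2. Efficacy and disposition stay by assigned treatment.
3. Every participant for whom the two differ is listed.
4. Mixed exposure follows a prespecified rule that does not move events that began before the first active dose into the drug column. For example, place the participant by the treatment taken for most of the dosing period, keep any such earlier events out of the drug column, and flag or list events by the treatment being taken at onset. Because drug is dispensed at Day 1 and Week 4 of an 8-week period, one wrong kit can split exposure about evenly, so the rule needs a tie-break.

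A simpler rule, such as the highest active dose taken, would put events from a placebo period into the drug column after one wrong kit at Week 4. That recreates the problem.

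Record the change in SAP 10.1, since Protocol Table 14 lists ECG abnormalities by assigned group. The cost is a little extra programming and the mixed-exposure rule to specify. The sample size is unchanged. Settling it before unblinding avoids a later choice about which column holds an event.

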5.3. Analysis Populations

5.3.1. Full Analysis Set

The FAS includes all participants enrolled in the study who received at least 1 dose of study drug.

The FAS will be used for the summary of demographics, baseline characteristics, participant disposition, and analyses of all efficacy and safety data.

[REDACTED]

6. BASELINE, EXPOSURE, AND DISPOSITION VARIABLES AND ANALYSES

6.1. Baseline and Demographics, Physical Characteristics, and Disease History

6.1.1. Demographics

The following demographics will be summarized for the FAS: age, sex, race, ethnicity, weight, height, and BMI.

6.1.2. Baseline Disease Characteristics

The following baseline disease characteristics will be summarized for the FAS:

- Days since first onset of HS;
- Stable disease at least 90 days before screening (Yes/No);
- Other autoimmune disorders (Hyperlipidemia/Hypertension/Diabetes/Abdominal obesity/Arthritis/IBD: Crohn disease/IBD: Ulcerative colitis/Psoriasis/Spondylarthropathy/PCOS/Other/None).

6.1.3. Prior Therapy

Prior medication information for HS will be used to identify medication received by participants before enrollment into the study. Prior medications for HS will be summarized.

6.1.4. General Medical History

For participants in the FAS, general medical history will be summarized by assigned treatment group. This summation will include the number and percentage of participants with significant medical history for each body system/organ class as documented on the eCRF.

6.2. Disposition of Participants

The number and percentage of participants who were enrolled, randomized, treated, completed the study, discontinued study treatment with a primary reason for discontinuation, and discontinued from the study with a primary reason for withdrawal will be summarized for the FAS. The number of participants randomized/enrolled by site will also be provided by treatment group.

6.3. Protocol Deviations

Protocol deviations recorded on the eCRF will be presented in the participant data listings and tables.

6.4. Exposure

For participants in the FAS, descriptive statistics will be provided by treatment group for duration of treatment, average daily dose, and total dose. Duration of treatment with INCB054707 is defined as the number of days from Day 1 to the date of last record of INCB054707 administration.

6.5. Study Drug Compliance

For participants in the FAS, overall compliance (%) for INCB054707 will be calculated for all participants as

Compliance (%) = $100 \times [\text{total number of tablets dispensed} - \text{total number of tablets returned}] / [\text{total intended number of tablets}]$.

- The total intended number of tablets will be based on the earliest study day of permanent discontinuation of the study drug or last study drug record in the database.

6.6. Prior and Concomitant Medication

For participants in the FAS, prior medications and concomitant medications will be coded using the WHO Drug Dictionary and summarized by WHO drug class and WHO drug term. Results will be summarized as number and percentage of participants with prior and concomitant medications by preferred term and WHO drug class.

7. EFFICACY

All efficacy analyses are exploratory. Hence, no p-values will be provided and multiple adjustment will not be made.

[Appendix A](#) provides a list of planned tables, figures, and listings.

7.1. Efficacy Parameters

An example of the lesion count worksheet is provided in the Study Manual and will be used for assessment of Hurley Stage, HiSCR, modified Sartorius scale, [REDACTED]. It includes assessment of 12 anatomic regions:

- left/right axilla,
- left/right sub/inframammary area,
- intermammary area,
- left/right buttock,
- left/right inguino-crural fold,
- perianal area, perineal area,
- and other areas.

Additionally, the need for rescue lesional treatment, including number of interventions, will be documented in this worksheet.

7.1.1. Hurley Stages of Hidradenitis Suppurativa

Hurley Stages of HS are defined in [Table 2](#). The investigator will determine the Hurley Stage in each affected anatomical region at the designated study visits. If more than 1 stage is present in a region, the worst stage in each region should be documented. The participant is assigned Hurley Stage corresponding to the Hurley Stage of his or her worst involved anatomic region.

Table 2: Hurley Stages of Hidradenitis Suppurativa

Stage	Description
I	Abscess formation (single or multiple) without sinus tracts and cicatrization
II	Recurrent abscesses with tract formation and cicatrization; single or multiple, widely separated lesions
III	Diffuse or near-diffuse involvement or multiple interconnected tracts and abscesses across the entire area

7.1.2. Hidradenitis Suppurativa Clinical Response (Abscess and Inflammatory Nodule Count)

A HiSCR definition is based on the following criteria relative to the baseline at each visit:

- at least 50% reduction in total of counts of the abscess and inflammatory nodule, and
- no increase in abscess count, and
- no increase in draining fistula count (refer to the Study Manual; [Kimball et al 2016](#)).

7.1.3. Modified Sartorius Scale

The modified Sartorius scale is a measure of the severity of HS (refer to the Study Manual; [Sartorius et al 2003](#)). A larger score denotes a more severe disease status. The total Sartorius score is the sum of 12 anatomic region Sartorius scores. The regional Sartorius score can be calculated as follows, using the parameters in [Table 3](#):

Regional Sartorius Score = Region + (2 × Number of Inflammatory Nodules) + (2 × Number of Non-Inflammatory Nodules) + (4 × Number of Abscesses) + (4 × Number of Draining Fistulas) + (4 × Number of Non-Draining Fistulas) + (1 × Number of Hypertrophic Scars) + Distance + Separate.

Table 3: Sartorius Score

Region	0	Otherwise
	3	If any lesion count in this anatomic region > 0
Distance	0	If no active lesion
	2	If longest distance between two relevant lesions or size < 50 mm
	4	If longest distance between two relevant lesions or size ≥ 50 mm and < 100 mm
	6	If longest distance between two relevant lesions or size ≥ 100 mm
Separate	0	If all lesions clearly separated by normal appearing skin
	6	Otherwise

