5.1. Inclusion Criteria

Participants are eligible to be included in the study only if all of the following criteria apply:

1. Men and women aged 18 to 75 years at the time of consent.
2. Diagnosis of HS (confirmed by a dermatologist) with a disease duration of at least 6 months before screening.
3. Stable course of HS for at least 90 days before screening, as determined by the investigator.
4. HS lesions present in at least 2 distinct anatomic areas, 1 of which must be Hurley Stage II (ie, recurrent abscessed with tract formation and cicatrization; single or multiple, widely separated lesions) or Hurley Stage III (ie, diffuse or near diffuse involvement, or multiple interconnected tracts and abscesses across the entire area) at screening.
5. Total AN count of at least 3 at screening and baseline.
6. Willingness to avoid pregnancy or fathering children based on the criteria below:
 - a. Male participants must agree to take appropriate precautions to avoid pregnancy (with at least 99% certainty) from screening through 90 days after the last dose of study drug. Male participants must also refrain from donating sperm during this period. Permitted methods that are at least 99% effective in preventing pregnancy (see [Appendix A](#)) should be communicated to the participant and his understanding confirmed.

- b. Women of childbearing potential must have a negative serum pregnancy test at screening and a negative urine pregnancy test before the first dose on Day 1 and must agree to take appropriate precautions to avoid pregnancy (with at least 99% certainty) from screening through safety follow-up. Permitted methods that are at least 99% effective in preventing pregnancy (see [Appendix A](#)) should be communicated to the participants and their understanding confirmed.
- c. Women of nonchildbearing potential (ie, surgically sterile [hysterectomy, bilateral oophorectomy, or bilateral salpingectomy] OR postmenopausal, defined as ≥ 12 months of amenorrhea before screening without an alternative medical cause, confirmed by FSH levels at screening) are eligible.

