8.2.3. Modified Sartorius Scale

The modified Sartorius scale is a measure of the severity of HS (refer to the Study Manual; [Sartorius et al 2003](#)).

Points are given as follows for each body area: 2 points for each nodule (both inflammatory and noninflammatory); 4 points for each abscess; 4 points for each fistula (both draining and nondraining); 1 point for each scar; 2 to 6 points for the longest distance between 2 lesions or 0 points if no lesions; and 6 points if lesions are not separated by normal skin or 0 points if lesions are separated by normal skin. The "other area" only with the highest modified Sartorius scale at baseline will be calculated, and the same area should be evaluated throughout the study. The total modified Sartorius scale score is the sum of the 12 anatomic region scores.

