7.2. Analysis of Efficacy Endpoints

The efficacy endpoints include:

- Proportion of participants with a HiSCR (at least 50% reduction in AN count with no increase in abscess count and no increase in draining fistula count relative to baseline) at each visit;
- Proportion of participants achieving an AN count of 0 to 2 at each visit;
- Mean change from baseline in the HS Pain NRS scores, worst and average pain, at each visit;
- Mean change from baseline to Week 8 in the modified Sartorius scale score;
- Mean change from baseline in the number of draining fistulas count at each visit;
- Proportion of participants at each category of Hurley Stage at baseline and Week 8;
- Proportion of participants with change from baseline in Hurley Stage at Week 8;
- Proportions of participants in each HS-PGIC category during the treatment period;
- Actual measurements in HS-PGIC at each visit;
- Proportion of participants requiring rescue lesional treatment;
- Number of interventions with rescue lesional treatment;
- Proportion of participants at each scoring category of DLQI at each visit;
- Mean change from baseline in DLQI total scores at each visit;

[REDACTED]

Category variables will be summarized using descriptive statistics, including sample size, frequency, and percentages. Continuous variables will be summarized using descriptive statistics, including sample size, mean, median, standard deviation, standard error of the mean, minimum, and maximum.

[REDACTED]

[REDACTED]

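### SAP Table 3 gives the Sartorius Separate item no no-lesion row, so a fully cleared region scores 6 instead of 0 if the rule is coded as a literal if/else

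*SAP*

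**What the plan says.** SAP 7.1.3 builds a regional score from weighted lesion counts plus three items defined in Table 3: Region, Distance and Separate. It then adds the regions: "The total Sartorius score is the sum of 12 anatomic region Sartorius scores".

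The three items treat an empty region differently:

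- **Region** gives 3 points "If any lesion count in this anatomic region > 0"; its catch-all is 0.
- **Distance** has an explicit row, "If no active lesion", worth 0.
- **Separate** gives 0 "If all lesions clearly separated by normal appearing skin"; its catch-all is 6. There is no third row.

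Protocol 8.2.3 words the separation item with two specific conditions: "6 points if lesions are not separated by normal skin or 0 points if lesions are separated by normal skin". It has no catch-all. For distance it does name the empty case: "2 to 6 points for the longest distance between 2 lesions or 0 points if no lesions".

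The endpoint that uses the score is listed in SAP 7.2: "Mean change from baseline to Week 8 in the modified Sartorius scale score". SAP 10.1 declares no departure from the analyses in the protocol.

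**The concern.** Separate is the only one of the three items whose catch-all is its maximum. In the protocol, 6 points require lesions that run together. In the SAP table, 6 points become the default for anything not recorded as separated.

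For a region with no lesions, the question whether the lesions are separated has no natural answer. If the field is then blank, negative or not applicable, and the program follows the table literally, the region receives 6 points. That would sit badly with the SAP's own statement in the same section that higher scores mean worse disease.

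What is at stake is the change to Week 8. A region that loses all its lesions would keep or gain 6 points on this item, so its improvement would be understated. Any such loss would fall where regions clear.

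**Working it through.** The documents give no figure that depends on this item, so there is none to reproduce. The check applies the SAP's regional formula to a region before and after it clears.

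**Inputs**

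- Regional score (SAP 7.1.3) = Region + 2 × (nodules of either kind) + 4 × (abscesses + fistulas of either kind) + 1 × (hypertrophic scars) + Distance + Separate.
- Region = 3 with any lesion, otherwise 0. Distance = 0 with no active lesion, 2 if below 50 mm. Separate = 0 or 6 (SAP Table 3).
- 12 regions are summed (SAP 7.1.3).
- Entry requires "HS lesions present in at least 2 distinct anatomic areas" (Protocol 5.1), so up to 12 − 2 = 10 regions can be lesion-free at baseline.
- About 9 participants per dose level (SAP 3.3).
- Assumed for the examples: distance below 50 mm, and a lone nodule counted as separated.

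**A fully cleared region** (Region + counts + Distance + Separate)

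- Literal if/else, with separation not recorded: 0 + 0 + 0 + 6 = 6.
- No lesion scored as 0: 0 + 0 + 0 + 0 = 0.

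**Change when the region clears**

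| Region at baseline | Baseline score | Change, no lesion = 0 | Change, literal if/else | Share of that region's change lost |
|---|---|---|---|---|
| Two abscesses, separated | 3 + 8 + 2 + 0 = 13 | 0 − 13 = −13 | 6 − 13 = −7 | 6/13 = 46% |
| Two inflammatory nodules and one abscess, separated | 3 + 4 + 4 + 2 + 0 = 13 | −13 | −7 | 46% |
| The same lesions, not separated | 13 + 6 = 19 | −19 | 6 − 19 = −13 | 6/19 = 32% |
| One nodule | 3 + 2 + 2 + 0 = 7 | −7 | 6 − 7 = −1 | 6/7 = 86% |

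The loss is always 6 points per cleared region. The percentages refer to that one region, not to the 12-region total.

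**Regions never involved.** Under the literal coding each carries 6 points at both visits, and 6 − 6 = 0 in the change, provided the field is coded the same way both times. The level is raised by up to 10 × 6 = 60 points in a participant with two affected regions. A participant with no lesions anywhere would total 12 × 6 = 72.

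**Effect on an arm mean, for illustration.** One participant in an arm of 9 who clears two regions shifts the mean change by 2 × 6 / 9 = 1.3 points. The documents give no basis for how often regions will clear.

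**The case against.** The case against is substantial.

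- **The printed rule can give 0.** Read as strict logic, the condition that all lesions are separated is met when there are none. Under that reading the error is zero. This stands, and it is why the point is conditional.
- **The coding is not visible.** Both documents refer to the Study Manual for this scale, and to its lesion count worksheet. Either may set the entry for an empty region. This stands too, although the SAP prints its own table as the scoring rule, so the default belongs there.
- **A blank is not automatically 6.** SAP 4.1.5 says that missing values are generally not imputed. On that rule a blank would be missing. This argues against 6 but does not produce 0; it adds a third possible result for the same cell.
- **The surrounding text points to 0.** The protocol's 6-point condition presupposes lesions, no change to the protocol's analyses is declared, and a higher score is meant to be worse. All true. These show what was probably intended, not what Table 3 says.
- **Few regions may be affected.** The score also counts non-inflammatory nodules, non-draining fistulas and hypertrophic scars. Protocol 2.1.2 describes scars, fistulas and sinus tracts as components that drug treatment is not expected to change. Lesions given rescue treatment must be counted as still present from then on (SAP 7.1.4). Regions with any of these would seldom reach zero in 8 weeks. This stands as a limit on size.

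A reader might go further and infer that the SAP definitely awards 6 points to every empty region, that 60 or 72 spurious points enter the endpoint, or that most of the improvement is erased. The documents do not support this. The first states one reading as fact. The second concerns the score level, whereas constants in never-involved regions cancel in the change. The third takes the single-nodule example, an extreme for one region, as if it were the total.

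**Conclusion.** The point holds as a conditional one of low severity. Table 3 lacks a no-lesion row for Separate and turns the protocol's specific 6-point condition into a catch-all. Coded literally on a recorded field, it understates improvement by 6 points for each region that clears completely. Coded with an empty region as separated, it does no harm.

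The size rests on two things the documents do not show: how the separation field is completed for an empty region, and how many regions lose every counted lesion by Week 8. If the literal coding is used, the direction is against whichever arm clears more regions, but no estimate of that bias is possible from the documents.

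The reach is narrow. The modified Sartorius change is one of several descriptive secondary endpoints, without p-values (SAP 7) or alpha control (SAP 3.2). The primary safety analysis, HiSCR and the AN count do not use this item.

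**What to change.** In SAP Table 3, define Separate in line with Protocol 8.2.3:

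- 0 if the region has no lesion;
- 0 if lesions are present and normal-looking skin clearly separates all of them;
- 6 only if lesions are present and that is not the case.

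It also helps to state that a blank separation field in a region with lesions is treated as missing, so that the catch-all is not used for it.

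The cost is a small edit to one table, with a matching line in the programming specification. No additional data are needed.
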